The protocol, informed consent form, recruitment materials, and all participant materials have been submitted to the IRB for review and approval. Approval of both the protocol and the consent form will be obtained before any participant is enrolled. Any amendment to the protocol will require review and approval by the IRB before the changes are implemented to the study. All changes to the consent form will be IRB-approved; a determination will be made regarding whether a new consent needs to be obtained from participants who provided consent, using a previously approved consent form.

1 PROTOCOL SUMMARY**1.1 SYNOPSIS**

Title: *Nutrition and Prostate Cancer: Assessing the Clinical Response of Prostate Cancer to Fermented Soy*

Study Description: This is a parallel group, double blind, randomized, controlled trial to assess the efficacy of a fermented soy product (Q-CAN® Plus or “QC”) vs. placebo, in 72 adults with localized prostate cancer prior to prostatectomy. We propose a line of inquiry to assess the effects of QC in humans, assessing immunological and clinical parameters.

Objectives: **Primary Objective:** To assess the efficacy of QC vs. placebo in 72 adults with localized prostate cancer prior to radical prostatectomy.

Secondary Objectives: To assess the efficacy of QC on disease progression, prostate cancer biomarkers, and quality of life.

Endpoints: **Primary Endpoint:** Serum PSA (prostate specific antigen)

Secondary Endpoints:

1. Volume of prostate gland
2. Volume of biopsy-proven, index prostate cancer (PCa) lesion
3. Gleason score compared to preoperative biopsies
4. PCa tissue telomeric DNA length
5. Cancer of the Prostate Risk Assessment (CAPRA-S) post-surgical score

6. Cell cycle progression score assessment of PCa mRNA
7. Specific marker changes on PCa tissue microarrays using automated quantitative analysis (AQUA)
8. Functional Assessment of Cancer Therapy – Prostate (FACT-P 4[©])

Study Population: The study population (N=72) will consist of men with histologically verified prostate cancer (at any stage) aged 18 years and older, scheduled for radical prostatectomy within 4-10 weeks at Yale New Haven Hospital in New Haven, CT, or Lawrence+Memorial Hospital in New London, CT, or South County Hospital in Wakefield, RI.

Phase: Phase 3 trial

[figure not shown]
Description of Sites/Facilities Enrolling Participants: This is a multi-site study being conducted at Yale University School of Medicine, New Haven, CT, Lawrence+Memorial Hospital in New London, CT, and South County Hospital in Wakefield, RI, USA. The Yale New Haven Health System (YNHHS) is a non-profit healthcare system with corporate headquarters in New Haven, CT. Yale New Haven Health operates five delivery networks, one of which is Lawrence+Memorial Hospital (LMH). South County Hospital (SCH) is an independent, non-profit acute care hospital serving southern Rhode Island. All study urologists/Co-Investigators have appointments in Yale University School of Medicine.

Description of Study Intervention: We will assess the efficacy of a fermented soy extract in a placebo-controlled study of 72 adult males with localized prostate cancer. Over the course of 4-10 weeks (between baseline and prostatectomy), subjects will consume two 12.5-gram packets of soy or matched dose placebo per day.

Study Duration: 36 months

Participant Duration: The time it will take for each individual participant to complete all participant visits will vary (4-10 weeks), depending on the surgery date of each individual's prostatectomy.

1.2 SCHEMA

Flow diagram of Study Schema

^a Duration in the study varies (between 4-10 weeks), and is dependent upon each subject's date for surgery.

1.3 SCHEDULE OF ACTIVITIES (SOA)

Procedures	Screening/Baseline Day -7 to -1	Study Visit 1 Day 1 +/-3 days	Phone Assessment 1 Day 7 +/-1 day	Phone Assessment 2 Day 14 +/-1 day	Phone Assessment 3 Day 21 +/-1 day	Phone Assessment 4 Day 28 +/-1 day	Phone Assessment 5 Day 35 +/-1 day	Phone Assessment 6 Day 42 +/-1 day	Phone Assessment 7 Day 49 +/-1 day	Phone Assessment 8 Day 56 +/-1 day	Phone Assessment 9 Day 63 +/-1 day	Phone Assessment 10 Day 70 +/-1 day	Final Study Visit 2 Day 77 +/-1 day
Informed consent	X												
Demographics	X												
Medical history	X												
Anthropometrics (height, weight)	X												
Concomitant medication review	X	X	X	X	X	X	X	X	X	X	X	X	X
Soy consumption inventory	X												
FACT-P QoL questionnaire	X												X
Serology [†]	X												X
Randomization/Enrollment	X												
IP dispensed		X											X
IP consumed ^{††}		X	X	X	X	X	X	X	X	X	X	X	X
Weekly telephone calls ^{††} assessing adherence/IP accountability, safety			X	X	X	X	X	X	X	X	X	X	X
Adverse event review and evaluation			X	X	X	X	X	X	X	X	X	X	X
Other laboratory assessments ^{†††} (Telomere assay, CCP, AQUA)													

[†] Amylase, CBC with diff, CMP, CRP, estrogen, ESR, IGF-1, IGFBP-1, IGFBP-2, IGFBP-3, lipase, lipid panel, PHI (prostate health index - includes PSA), testosterone (total, bioavailable and free), and TSH.

^{††} Duration in the study varies (between 4-10 weeks), and is dependent upon each subject's date for surgery.

^{†††} Biopsied prostate tissue (pre-enrollment) and the excised prostate are biobanked by pathology outside the clinical trial's schedule of activities, regardless of participation. At Screening/Baseline, participants are consented for analysis of their frozen prostate tissue (to conduct the telomere assay, CCP, and AQUA laboratory assessments) after the study has concluded enrollment.

2 INTRODUCTION

2.1 STUDY RATIONALE

Prostate cancer is the most commonly diagnosed non-cutaneous cancer in men in the Western world. Prostate cancer is often localized and grows slowly, so men may live for many years with the disease. However, some forms of prostate cancer may behave more aggressively and is an important cause of morbidity and mortality. Given the protracted, yet potentially fatal, natural history of the disease, there is growing interest in low-toxicity interventions in the tertiary prevention of morbidity and mortality due to prostate cancer.¹

2.2 BACKGROUND

Soy Isoflavones and Prostate Cancer

Genistin is an isoflavone found in a number of dietary plants such as soy. Genistin is also converted to a more familiar *genistein*, thus, the biological activities including anti-atherosclerotic, estrogenic and anticancer effects are analogous.

Genistin, genistein and other isoflavones have been identified as angiogenesis inhibitors, and found to inhibit the uncontrolled cell growth of cancer, most likely by inhibiting the activity of substances in the body that regulate cell division and cell survival (growth factors). Various studies have found that moderate doses of genistein have inhibitory effects on cancers of the prostate, cervix, brain, breast, and colon.^{2,3}

Studies on rodents have found genistein to be useful in the treatment of leukemia, and that it can be used in combination with certain other anti-leukemic drugs to improve their efficacy.⁴

A recent systematic review assessed the role of genistein in prostate cancer, where the effect of genistein supplementation was investigated in two studies. In men randomized to 30 mg genistein daily for three to six weeks prior to prostatectomy, differences in favor of the experimental, versus control, group were reported for percentage change in PSA ($p = 0.051$), cellular response ($p = 0.033$), and cell proliferation ($p < 0.001$). However, the trial was assessed as having high or unclear risk of bias on four of the seven criteria, and it was assessed to have low risk of bias for sequence generation and blinding of participants, as well as selective outcome reporting.⁵ Comparably, in a trial with relatively low risk of bias, in men undergoing watchful waiting, randomization to 60 mg genistein daily versus an isocaloric placebo for 12 weeks had no impact on mean change in PSA.¹

Q-CAN® Plus and Fermented Soy

There is an emerging literature demonstrating bioactive effects of ZhenHua 851 (Q-CAN® Plus or “QC”), a fermented soy food in humans. Uncontrolled studies and case reports support benefits in cancer progression and changes in activation markers in humans’ immune cells including changes in expression of CD3, CD4, and CD8 markers, as well increased NK cell activity. These are generic changes in immune activation and are associated with increased anti-cancer activity. Case reports associate consumption of QC with reduced prostate specific antigen (PSA) velocity in men with prostate cancer. Fermented soy products are reported to have increased isoflavone concentration⁶ compared to standard soy foods, and may contain a rich mixture of probiotic species.

Yang et al. reported that 13-methyltetradecanoic acid (13-MTD), a possible active ingredient in QC, inhibited growth of various cancer cell lines through the induction of apoptosis without adverse effects.⁷ Furthermore, Lin et al. found induction of mitochondrial-mediated apoptosis through regulation of the AKT and MAPK pathways.⁸ Most recently, Cai et al. reported that 13-MTD inhibits proliferation and induces apoptosis through the down-regulation of AKT phosphorylation followed by caspase activation.⁹

Identifying the anti-cancer profile of QC in human cancer cell lines

13-MTD has been demonstrated to induce apoptosis of a range of human cancer cell lines (HT-29-colon, MCF7-breast [estrogen sensitive], MDA-MB-231-breast [estrogen insensitive], LNCaP-prostate [androgen sensitive], DU 145-prostate [androgen insensitive], NCI-SNU-1-stomach, SNU-423-liver, NCI-H1688-lung, BxPC3-pancreas) in a concentration range of 10-25 μ g/ml.⁷ The reductionist approach of testing a single metabolite in QC is helpful as it can provide mechanistic insight into the biological actions. It also has disadvantages, and primary among these is that beneficial effects of QC may be due to the combinations of effects of the QC metabolites, and such effects will be missed when only single metabolites such as 13-MTD are investigated.

Preliminary Studies Conducted at the Yale School of Medicine

We have recently produced data showing that 13-MTD can reduce IL-6 production from activated macrophages. As IL-6 contributes to the development of cachexia, this may result in a beneficial clinical response in addition to any direct anti-tumor effects.

Our team recently completed a comprehensive independent analysis of QC.¹⁰ In order to validate the Certificate of Analysis, the soy test agent (QC) underwent quarantine and independent third party laboratory analysis (product characterization) for: total soy isoflavones and essential fatty acids, aflatoxins, authenticity (GMO status), microbial contamination, heavy metals, residual solvents and herbicides, pesticides and fungicides. Selected, individual methods are referenced in the results section under their corresponding tables. Q-CAN® Plus contained 290.12 mg of total soy isoflavones and 5.48 g of total fatty acids per 240 ml. Qualitative PCR assays for CaMV 35s promoter and MON89788 RR2 soybean were negative, indicating that no soy genetically modified organisms were present. Aflatoxins were not detected. *Enterobacteriaceae*, *E. coli*, *Salmonella* (spp), *S. aureus*, *Pseudomonas aeruginosa*, mold and yeast were absent, demonstrating a sterile product. A profile of 300 herbicides, pesticides and fungicides was negative and none of the 52 chemical residual solvents tested above the limit of quantification. Lead, mercury, arsenic, and cadmium were all below the detectable limit (5-10 ppb). Among the isoflavones isolated in significant quantities were genistein and genestin. In this independent evaluation, the manufacturer's Certificate of Analysis was validated.

We are currently assessing data from the consumption of QC in 10 lean and 10 obese, otherwise healthy adults (Yale HIC/IRB #1507016139). During the 14-week study, participants consumed 16oz of QC daily for 4 weeks (week 3 through week 7). The oral and fecal microbiome of each participant was assayed starting at baseline, from saliva and stool samples. Samples were collected once a week, for the first 7 weeks of the study, then every other week for the remainder of the study. This sampling regimen is intended to reveal any changes in the microbiome due to consumption of QC and the persistence of any changes for 7 weeks after cessation of QC. Blood was also collected at 8 time points throughout the study to assay activation of the inflammasome machinery in peripheral blood cells. Results from these microbiome and blood assays are being compared between the lean and obese groups. Other measures of the study included BMI and a 24-hour dietary recall. The study closed to enrollment when targeted accrual was met in August 2017. We are performing ongoing correlative laboratory testing of specimens obtained in blood and stool.

Based on participant reports in the preliminary study, QC was both palatable and tolerable (only one participant withdrew), with no adverse effects besides some reports of mild gastrointestinal symptoms. Thus, the palatability and tolerability of the product dosing in the preliminary study (two 8-oz. bottles/day) serves, in part, as the basis for dosage in the proposed study. The product characterization (noted above) further justifies dosing for the proposed study, as the laboratory analysis demonstrated that this dose contains 141 mg of genistin and 26 mg of genistein per 8 oz. (240 ml) bottle.

We propose a line of inquiry to assess the effects of QC fermented soy consumption in humans, assessing immunological and clinical parameters.

2.3 RISK/BENEFIT ASSESSMENT**2.3.1 KNOWN POTENTIAL RISKS**

Immediate risks: There is a risk of allergic reaction to any soy product, such as hives, itching, abdominal discomfort, aversion and anaphylaxis. Persons allergic or sensitive to soy are excluded from the study. Participants in this study will be asked to consume GRAS foods - a brown rice-based placebo or fermented soy.

Preliminary testing indicated that Q-CAN® Plus oral liquid had no toxic effects, even when large doses were taken acutely. In our preliminary safety/tolerability study with healthy volunteers (N=20), some participants reported mild, short-lasting gastrointestinal symptoms with the daily intake of the fermented soy beverage: nausea (3), stomach pain (1), diarrhea (1), and bloating (4).

There is a small risk that when blood is drawn, participants may experience pain at the venipuncture site, bruising, or fainting, and in rare instances infection. This is very unlikely to occur, as all phlebotomists where subject visits will occur are trained, certified, and experienced in standard phlebotomy procedures.

Long-range risks: As with any trial, there is potential risk of loss of confidentiality; however, every effort will be made to keep participant information confidential, including study team training in GCP and HIPAA Privacy and Security, and limiting access to any related health information to only the small number of individuals who require access to carry out their role in the study.

2.3.2 KNOWN POTENTIAL BENEFITS

Immediate potential benefits: We anticipate beneficial changes in prostate condition in association with fermented soy consumption.

Long-range potential benefits: We hope that the results of the study will help researchers better understand the role of fermented soy in relation to its anti-tumor effects, signaling pathways in tumor cells, which will add to scientific knowledge in prostate cancer.

2.3.3 ASSESSMENT OF POTENTIAL RISKS AND BENEFITS

This is a minimal risk study; refer to Section 2.3.1, Known Potential Risks.

3 OBJECTIVES AND ENDPOINTS

OBJECTIVES	ENDPOINTS	JUSTIFICATION FOR ENDPOINTS
Primary		
To assess the efficacy of QC fermented soy vs. placebo in 72 adults with localized prostate cancer (PCa) prior to radical prostatectomy.	The primary assessment will be a comparison between participants in the QC arm vs. the placebo arm, in mean serum PSA (prostate-specific antigen) level changes, from baseline and time of admission for surgery.	Fermented soy supplementation/soy isoflavones are known to decrease serum PSA, the levels of which are used to indicate prostate health.

OBJECTIVES	ENDPOINTS	JUSTIFICATION FOR ENDPOINTS
Secondary	
To assess the efficacy of QC on disease progression (1, 2, 3, 4, 5), PCa biomarkers (6, 7), and quality of life (8).
 
1. Volume of prostate gland 2. Volume of biopsy-proven, index PCa lesion 3. Gleason score compared to preoperative biopsies 4. PCa tissue telomeric DNA length 5. Cancer of the Prostate Risk Assessment (CAPRA-S) score 6. Cell cycle progression score assessment of prostate cancer mRNA from PCa tissue 7. Specific marker changes on PCa tissue microarrays (TMAs) using AQUA - automated quantitative analysis 8. Functional Assessment of Cancer Therapy – Prostate (FACT-P v4[®])
	
1, 2, 3: Pathological investigation of the removed prostate gland, to analyze any modulation of PCa grade (Gleason score) compared to preoperative biopsies, volume of gland and of biopsy-proven, index prostate cancer lesion, and extent (involvement of surgical margins and extraprostatic extension) of clinical and pathological tumor stage and degree of tumor focality.
 
4. Analysis of telomere length in research samples of human peripheral blood mononuclear cells reveals that telomere length decreases with increased replication of cells, reflecting the replicative history of those cells.
 
5. Post surgical/post intervention CAPRA score for comparison with baseline
 
6. Cell cycle progression score assessment of PCa mRNA (from PCa tissue before and after treatment and between treatment arms) is a novel RNA expression-based assay that directly measures tumor cell growth characteristics in order to stratify patients with localized PCa according to disease aggressiveness.
 
7. AQUA can assess TMAs using fluorescent tags to define tumors, localize sub-cellular compartments, and grade intensity of specific markers on a continuous scale.
 
8. Quality of life assessment for men with PCa

4 STUDY DESIGN

4.1 OVERALL DESIGN

We hypothesize that QC fermented soy is beneficial in adults with prostate cancer on the basis of prior anti-cancer activity in human prostate cancer cell lines.

This is a parallel group, double-blind, randomized, phase III clinical trial. The primary aim is to assess the efficacy of Q-CAN (QC) fermented soy vs. placebo in 72 adults with prostate cancer. Subjects will be randomized to one of two arms (n=72; 36 per arm), and stratified (low/high) based on Cancer of the Prostate Risk Assessment¹¹ (CAPRA) score: 0-4=low/intermediate risk, 5-10=high risk). The two arms are:

1. **Intervention:** Daily QC (two 12.5g packets/day) (~1 ounce/day) taken between the time of enrollment and radical prostatectomy.
2. **Control:** Daily (matched dose) placebo, taken between the time of enrollment and radical prostatectomy.

This is a multi-site trial. Clinical assessments (3 study visits) will take place either in the Yale Center for Clinical Investigation's Research Outpatient Unit, or in LMH's urology clinic space, or South County Hospital (SCH) urology clinic space (as determined by the referring physician's location), at: 1) screening/baseline, 2) enrollment (~1-3 days after BL), and 3) just prior to prostatectomy, *estimated* at between 4 and 10 weeks from baseline/enrollment (see section 1.3 SOA). Length of time in the study will vary for each subject, depending on how far out their prostatectomy will occur; all prostatectomies will be scheduled to occur between 4-10 weeks post-baseline.

To minimize bias, the Medical Informatics Group will handle randomization through Yale's Clinical Trial Management System, OnCore® (Forte Research Systems, Inc., Madison, WI). The blinded study coordinator will access the OnCore® system to indicate eligibility status based on inclusion/exclusion criteria. The assignment will then be retrieved by a blinded OnCore® Statistician, who will perform randomization. Once the participant has been successfully randomized to a treatment arm, the statistician will send confirmation to the pharmacy for dispensing, and also inform the study coordinator. Once made, the assignment is final and the participant will be analyzed in that group regardless of future events or information, in accordance with the intent-to-treat principle.

For interim analysis details, refer to Section 9.4.6, Planned Interim Analysis.

4.2 SCIENTIFIC RATIONALE FOR STUDY DESIGN

The design and rationale for this study are informed by and based on the work of Lazarevic et al.⁵

4.3 JUSTIFICATION FOR DOSE

Based on participant reports in the preliminary study, QC was both palatable and tolerable (only one participant withdrew), with no adverse effects besides some reports of mild gastrointestinal symptoms. Thus, the palatability and tolerability of the product dosing in the preliminary study (two 8-oz.

bottles/day) serves, in part, as the basis for dosage in the proposed study. The product characterization (as described in Section 2.2, Background) further justifies dosing for the proposed study, as the laboratory analysis demonstrated that this dose contains 141 mg of genistin and 26 mg of genistein per 8 oz. (240 ml) bottle.

4.4 END OF STUDY DEFINITION

A participant is considered to have completed the study if he has completed all study visits (including participation in the weekly phone calls to assess daily IP intake), as shown in Section 1.3, Schedule of Activities. The end of the study is defined as completion of the last subject's final study visit.

5 STUDY POPULATION

5.1 INCLUSION CRITERIA

In order to be eligible to enter this study, an individual must meet all of the following criteria:

- 1) Histologically verified Prostate Cancer (at any stage)
- 2) Age \geq 18 years
- 3) Scheduled to be treated by radical prostatectomy within the next 4-10 weeks
- 4) Understanding and willingness to provide consent

5.2 EXCLUSION CRITERIA

An individual who meets any of the following criteria⁵ will be excluded from participation in this study:

- 1) Previous (within 6 months of enrollment) or concurrent hormonal therapy or chemotherapy; specifically, treatment with 5-alpha reductase inhibitors (finasteride and dutasteride).
- 2) History of hormone dependent malignancies
- 3) Concomitant thyroid disease or currently taking thyroid hormone replacement medication
- 4) Current high-dose soy consumption, micronutrient, or herbal supplements, on soy or vegetarian nutrition, or any other extreme dietary habits
- 5) Current or past history of any liver or pancreas disease
- 6) History of hypersensitivity to soy-containing products
- 7) Malabsorption conditions that might interfere with absorption of the investigational product

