6.2.2 FORMULATION, APPEARANCE, PACKAGING, AND LABELING

The intervention product is Q-CAN® Plus, a fermented soybean-derived phytochemical liquid food supplement in a freeze-dried version. Q-CAN® is a commercially available GRAS beverage that has been marketed in China since 1985 and in the United States since 1991. In the US, it is marketed as a food, under Fujian Yang Zhenhua 851 Bio-Science Co., Ltd., registration number 17334630796. The active ingredient is soybean (22%), and primary constituents of the formulation are isoflavones genistin, daidzin genistein, and daidzein. The freeze-dried powder consists of fermented soy (78.2%), soy extract (1.8%), natural chocolate flavor (18%), and *Siraitia grosvenorii* (2%).

The placebo product for this trial will be a brown rice flour-based powder, matching in color and consistency with the intervention product. The placebo will contain the same flavoring (natural chocolate flavor, 18%) and sweetener (*Siraitia grosvenorii*, 2%) as the intervention, for dual purposes of matching taste (to the greatest degree possible) and masking the difference in flavor between fermented soy and brown rice powders.

Fujian Yang Zhenhua 851 Bio-Science Co., Ltd./BESO Biological Research Center, Inc., will manufacture the intervention and placebo products. The immediate packaging for both will be a sealed foil pouch, as shown below:

Nutrition and Prostate Cancer Yale IRB/HIC #2000020868
Q-CAN Plus Fermented Soy or Placebo Net weight: 12.5 g per packet
Directions for Use: Dissolve powdered contents with about 8 oz. of water; stir until dissolved, then consume.
Once powder has been added to liquid, either consume or store in refrigerator.
Caution: New Drug – Limited by Federal (or United States) law to investigational use.
Storage Conditions: Store unopened packets in cool, dry location. Once powder has been added to liquid, either consume or store in refrigerator.
Contact: [name] (Principal Investigator) at [contact] or [name] (Clinical Trials Manager) at [contact]
Lot #:
Expiration date:
BESO Biological Research Center, Inc. Diamond Bar, CA

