8.2 SAFETY AND OTHER ASSESSMENTS

Sequence of events to occur during the screening process and any decision points regarding participant eligibility: refer to Section 8.1, Efficacy Assessments

Time frame prior to enrollment within which screening procedures/evaluations must be performed: refer to Section 8.1, Efficacy Assessments

Procedures and evaluations to be done as part of the study to support the determination of safety include:

- **Biological specimen collection and laboratory evaluations -**
 - Screening/Baseline Serology (to ensure patients' laboratory results are within acceptable range for study participation): CRP (C-reactive protein), lipase, lipid panel, amylase, TSH (thyroid stimulating hormone), ESR (erythrocyte sedimentation rate), CBC with Diff (complete blood count with differential), and CMP (comprehensive metabolic panel). These tests will be repeated at Visit 2 to ensure deleterious changes have not occurred and that patients' laboratory results are within acceptable range prior to prostatectomy (refer to Section 1.3, SOA for complete serology list).
 - Nursing staff and phlebotomists at all sites are trained and certified in standard phlebotomy techniques.
 - Total volume of blood to be drawn at Screening/Baseline and at Visit 2 is approximately 20-30 cc.
- **Administration of questionnaires, instruments and patient-reported outcomes** – refer to Section 8.1, Efficacy Assessments
- **Counseling procedures, including any dietary or activity considerations** - During this study, participants may maintain their current diet and level of physical activity to which they are accustomed, i.e., they will not be asked to abstain from small amounts of soy in their diet. (At time of phone screening, individuals who reported current high-dose soy consumption, use of herbal supplements, or soy or vegetarian nutrition, or any other extreme dietary habits – or soy allergy or sensitivity – would have been excluded from participation.) Participants will be given thorough dosing instructions for consuming the study drink, and will be asked to complete a daily dosing diary.

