8.3.3.3 EXPECTEDNESS

The principal investigator will be responsible for determining whether an adverse event (AE) is expected or unexpected. As with our preliminary safety/tolerability study of fermented soy consumption in healthy volunteers (N=20) we would expect that mild, intermittent gastrointestinal (GI) symptoms (nausea, stomach pain, diarrhea, and/or distension) could occur in a minority of participants, and would more likely become known after the first few doses, at the beginning of the study. While subjects will be screened for known allergy to soy, there is a risk of allergic reaction. An AE will be considered unexpected if the nature, severity, or frequency of the event is not consistent with symptoms as described here.

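### The hypersensitivity exclusion covers soy only, although the two study powders also contain brown rice flour, chocolate flavor and monk fruit

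*Protocol*

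**What the plan says.** **Eligibility.** Protocol 5.1 has four inclusion criteria, ending with "Understanding and willingness to provide consent"; none concerns allergy. Section 5.2 has seven exclusions, of which only the sixth does: "History of hypersensitivity to soy-containing products".

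**Risk and screening text.** Section 2.3.1 states: "There is a risk of allergic reaction to any soy product, such as hives, itching, abdominal discomfort, aversion and anaphylaxis". Its answer is the soy exclusion: "Persons allergic or sensitive to soy are excluded from the study". The next sentence of 2.3.1 names the brown-rice placebo as one of the two foods to be consumed, but attaches no allergy statement to it. Section 8.2 describes the telephone screen and includes "or soy allergy or sensitivity" among the reasons for exclusion. Section 8.3.3.3 says: "While subjects will be screened for known allergy to soy, there is a risk of allergic reaction".

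**Composition.** On the comparator, section 6.2.2 says: "The placebo product for this trial will be a brown rice flour-based powder, matching in color and consistency with the intervention product". The same section puts natural chocolate flavor (18%) and Siraitia grosvenorii (2%) in both powders, and 6.1.1 confirms that the flavor and sweetener are shared. The pouch label reproduced in 6.2.2 lists no ingredients.

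The SAP does not deal with eligibility. Its section 1 reports that the trial stopped before full enrollment.

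**The concern.** The protocol accepts that allergic reaction, up to anaphylaxis, is a risk of its product, and treats a known allergy as a reason not to randomize. It applies that reasoning to one ingredient only. The men assigned to placebo take a different base, and every man takes a flavor and a sweetener that no criterion mentions.

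What is at stake is an avoidable exposure. A man who already knows that he reacts to one of these ingredients could pass every written criterion and be given it daily for 4 to 10 weeks. The information needed to prevent this is in the protocol itself, in 6.1.1 and 6.2.2, but the eligibility section does not use it.

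**Working it through.** No stated figure has to be reproduced. The check sets the allergy text against the composition, with a little arithmetic on who is exposed.

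**1. What the allergy text covers**
- 5.1: no allergy item among four criteria.
- 5.2, item 6 of 7: soy.
- 2.3.1: soy.
- 8.2 (telephone screen): soy.
- 8.3.3.3: the screening clause names soy. The second clause, on the remaining risk of reaction, names no allergen, but it excludes nobody.

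The other exclusions do not reach the point. Item 4 concerns diet and supplement habits, and item 7 concerns malabsorption.

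**2. What the men take**
- Active powder: 78.2% fermented soy + 1.8% soy extract + 18% chocolate flavor + 2% monk fruit = 100%. The composition is complete.
- Placebo powder: brown rice flour base, with 18% chocolate flavor and 2% monk fruit.
- Daily amount (6.1.2): 2 × 12.5 g = 25 g in either arm. Chocolate flavor is 0.18 × 25 = 4.5 g and monk fruit is 0.02 × 25 = 0.5 g. These figures show that the exposure is real in both arms. They do not measure allergic risk.

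**3. Who could be exposed despite a known allergy**
- Flavor or sweetener: present in both powders, so exposure is certain for any randomized man who takes product.
- Rice: placebo only. With the planned 1:1 allocation (6.3), the chance is 36/72 = 50%. It is settled by randomization, after eligibility has been decided.

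**4. Whether another provision closes the gap**
- Medical history is taken at screening (1.3), and the referring urologist judges eligibility (8.1). Neither has a criterion under which a rice, chocolate-flavor or monk-fruit allergy excludes a man.
- The telephone screen (5.5) checks that no exclusion criterion is met, so it inherits the soy-only wording.
- The consent process (10.1.1) may inform the man, but it does not make his allergy an exclusion.
- Withdrawal (7.2) for an adverse event comes after exposure. Its ground for exclusion criteria that develop or come to light later would not apply, because this allergy is not an exclusion criterion.

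**5. Result.** Taken together, the sections admit a man with a known hypersensitivity to any of the three ingredients.

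**The case against.** The best reply is that the gap matters little in practice. Section 2.3.1 describes both products as GRAS foods, and nothing in the documents identifies rice, the flavor or monk fruit as an allergen of concern; the contents of the chocolate flavor are not given. A known allergy is something a man can report. He is telephoned, has his medical history taken, is referred by a urologist and goes through consent, and the consent form itself is not available to this review, so it cannot be assumed to omit the ingredients. Weekly calls and discretionary withdrawal follow.

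Much of this stands. It makes actual exposure much less likely than bare eligibility suggests, and it keeps the point at low frequency. It does not remove the gap, because each safeguard depends on someone acting without a written rule. GRAS status is no answer either: the soy product is called GRAS too, and soy hypersensitivity is still an exclusion.

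A reader might also infer more than the documents support:
- *Bias between arms.* Flavor and sweetener are at the same percentages in both powders, so they create no expected difference. Only rice differs, and with no prevalence given, an effect on the adverse-event comparison is speculation.
- *A serious adverse event for each case.* Section 8.3.2 sets criteria for seriousness. Hives, itching or abdominal discomfort need not meet them.
- *Loss of the final PSA.* Section 7.1 has staff attempt to collect final data after a man stops product, although it also bars new data after withdrawal, and 7.2 provides for replacement. Loss is possible but not established.
- *Risk that grows with total product taken.* Product mass summed over weeks says nothing about the chance of a reaction in a man who is already allergic. Nor is the exposure necessarily twice a day, since 6.1.2 lets the daily portion be taken all at once.

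**Conclusion.** The point holds as a gap between the eligibility text and the product composition. Soy is the only hypersensitivity that is screened or excluded, while planned placebo men (36 of 72) receive brown rice flour and all planned men receive chocolate flavor and monk fruit. A man with a known hypersensitivity to one of these is eligible as the criteria are written.

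Its size is small and cannot be put as a number of men, because the documents give no prevalence. It is a low-frequency patient-safety improvement that is worth making because it costs so little. It changes no estimate, error rate or power figure. Since enrollment ended early, its remaining use is in correcting the protocol text for any further use. The conclusion rests on the written criteria. Staff may have declined such men in practice, but nothing in the protocol required it.

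**What to change.** Reconcile exclusion 6 in section 5.2 with the composition in 6.1.1 and 6.2.2, so that the hypersensitivity exclusion covers the ingredients of both study products (soy, brown rice, natural chocolate flavor and Siraitia grosvenorii) and not soy alone. Bring the risk statement in 2.3.1, the telephone-screen description in 8.2 and the screening clause in 8.3.3.3 into line. The screen in 5.5 already works from the exclusion criteria, so the change to 5.2 carries into it without separate wording.

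The cost is one line in 5.2, matching edits elsewhere and one question in a call that already takes place. The downside is that very few otherwise eligible men would be excluded.
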